Appendix 4: modified Rankin Scale (mRS)

The Modified Rankin Scale (mRS)

(Use web calculator at www.modifiedrankin.com)

0 No symptoms

1 No significant disability; able to carry out all usual activities, despite some symptoms

2 Slight disability; able to look after own affairs without assistance, but unable to carry out all previous activities

3 Moderate disability; requires some help, but able to walk unassisted

4 Moderately severe disability; unable to attend to own bodily needs without assistance, and unable to walk unassisted

5 Severe disability; requires constant nursing care and attention, bedridden, incontinent

6 Dead

References:

Rankin J (May 1957). "Cerebral vascular accidents in patients over the age of 60. II. Prognosis". Scott Med J 2 (5): 200–15

Patel, N., et al. Simple and reliable determination of the modified Rankin Scale in neurosurgical and neurological patients: The mRS-9Q. *Neurosurgery*, published online in advance of print 26 July 2012

Appendix 5: EQ-5D-5L

Health Questionnaire

[figure not shown]
English version for the UK

© 2009 EuroQol Research Foundation. EQ-5D™ is a trade mark of the EuroQol Research Foundation. UK (English) v1.2

Under each heading, please tick the ONE box that best describes your health TODAY.

MOBILITY

| I have no problems in walking about I have slight problems in walking about I have moderate problems in walking about I have severe problems in walking about I am unable to walk about SELF-CARE | |
|--|--|
| I have no problems washing or dressing myself I have slight problems washing or dressing myself I have moderate problems washing or dressing myself I have severe problems washing or dressing myself I am unable to wash or dress myself | |
| USUAL ACTIVITIES (e.g. work, study, housework, family or leisure activities) I have no problems doing my usual activities I have slight problems doing my usual activities I have moderate problems doing my usual activities I have severe problems doing my usual activities I am unable to do my usual activities PAIN / DISCOMFORT | |
| I have no pain or discomfort I have slight pain or discomfort I have moderate pain or discomfort I have severe pain or discomfort I have extreme pain or discomfort | |
| ANXIETY / DEPRESSION I am not anxious or depressed I am slightly anxious or depressed I am moderately anxious or depressed I am severely anxious or depressed I am extremely anxious or depressed | |

© 2009 EuroQol Research Foundation. EQ-5D™ is a trade mark of the EuroQol Research Foundation. UK (English) v1.2

Appendix 6: National Institutes of Health Stroke Scale (NIHSS)

a Level of Consciousness

Instructions – Level of Consciousness (LOC): The investigator must choose a response if a full evaluation is prevented by such obstacles as an endotracheal tube, language barrier, orotracheal trauma/bandages. A 3 is scored only if the patient makes no movement (other than reflexive posturing) in response to noxious stimulation.

| Scale Definition | | | |
|------------------|--|--|--|
| 0 | Alert; keenly responsive. | | |
| 1 | Not Alert; but arousable by minor stimulation to obey, answer, or respond. | | |
| 2 | Not Alert; requires repeated stimulation to attend, or is obtunded and requires strong or painful stimulation to make movements (not stereotyped). | | |
| 3 | Responds only with reflex motor or autonomic effects, or totally unresponsive, flaccid, and areflexic. | | |

1b Level of Consciousness

Instructions – LOC Questions: The patient is asked the month and his/her age. The answer must be correct — there is no partial credit for being close. Aphasic and stuporous patients who do not comprehend the questions will score 2. Patients unable to speak because of endotracheal intubation, orotracheal trauma, severe dysarthria from any cause, language barrier, or any other problem not secondary to aphasia are given a 1. It is important that only the initial answer be graded and that the examiner not "help" the patient with verbal or non-verbal cues.

| Scale Definition | | | |
|------------------|-------------------------------------|--|--|
| 0 | Answers both questions correctly. | | |
| 1 | Answers one question correctly. | | |
| 2 | Answers neither question correctly. | | |
| | Score | | |

Level of Consciousness

Instructions – LOC Commands: The patient is asked to open and close the eyes and then to grip and release the nonparetic hand. Substitute another one-step command if the hands cannot be used. Credit is given if an unequivocal attempt is made but not completed due to weakness. If the patient does not respond to command, the task should be demonstrated to him or her (pantomime), and the result scored (i.e., follows none, one, or two commands). Patients with trauma, amputation, or other physical impediments should be given suitable one-step commands. Only the first attempt is scored.

| Scale Definition | | |
|------------------|----------------------------------|--|
| 0 | Performs both tasks correctly. | |
| 1 | Performs one task correctly. | |
| 2 | Performs neither task correctly. | |
| | Score | |

3

Score

Instructions: Only horizontal eye movements will be tested. Voluntary or reflexive (oculocephalic) eye movements will be scored, but caloric testing is not done. If the patient has a conjugate deviation of the eyes that can be overcome by voluntary or reflexive activity, the score will be 1. If a patient has an isolated peripheral nerve paresis (CN III, IV, or VI), score a 1. Gaze is testable in all aphasic patients. Patients with ocular trauma, bandages, pre-existing blindness, or other disorder of visual acuity or fields should be tested with reflexive movements, and a choice made by the investigator. Establishing eye contact and then moving about the patient from side to side will occasionally clarify the presence of a partial gaze palsy.

| Scale Definition | | | |
|------------------|--|-------|--|
| 0 | Normal. | | |
| 1 | Partial gaze palsy; gaze is abnormal in one or both eyes, but forced deviation or total gaze paresis is not present. | | |
| 2 | Forced deviation, or total gaze paresis is not overcome by the oculocephalic maneuver. | | |
| | | Score | |

Instructions: Visual fields (upper and lower quadrants) are tested by confrontation, using finger counting or visual threat, as appropriate. Patients may be encouraged, but if they look at the side of the moving fingers appropriately, this can be scored as normal. If there is unilateral blindness or enucleation, visual fields in the remaining eye are scored. Score 1 only if a clear-cut asymmetry, including quadrantanopia, is found. If patient is blind from any cause, score 3. Double simultaneous stimulation is performed at this point. If there is extinction, patient receives a 1, and the results are used to respond to item 11.

| Scale Def | Scale Definition | | |
|-----------|--|--|--|
| 0 | No visual loss. | | |
| 1 | Partial hemianopia. | | |
| 2 | Complete hemianopia. | | |
| 3 | Bilateral hemianopia (blind including cortical blindness). | | |

4

Score

Facial Palsy

Instructions: Ask — or use pantomime to encourage — the patient to show teeth or raise eyebrows and close eyes. Score symmetry of grimace in response to noxious stimuli in the poorly responsive or non-comprehending patient. If facial trauma/ bandages, orotracheal tube, tape, or other physical barriers obscure the face, these should be removed to the extent possible.

| Scale Definition | | | | | | |
|---|--|--|--|--|--|--|
| Normal symmetrical movements. | | | | | | |
| Minor paralysis (flattened nasolabial fold, asymmetry on smiling). | | | | | | |
| Partial paralysis (total or near-total paralysis of lower face). | | | | | | |
| Complete paralysis of one or both sides (absence of facial movement in the upper and lower face). | | | | | | |
| | | | | | | |

Score

[figure not shown]

Instructions: The limb is placed in the appropriate position: extend the arms (palms down) 90 degrees (if sitting) or 45 degrees (if supine). Drift is scored if the arm falls before 10 seconds. The aphasic patient is encouraged using urgency in the voice and pantomime, but not noxious stimulation. Each limb is tested in turn, beginning with the non-paretic arm. Only in the case of amputation or joint fusion at the shoulder, the examiner should record the score as untestable (UN) and clearly write the explanation for this choice.

| Scale Definition | | | | | | | | | |
|------------------|---|--|--|--|--|--|--|--|--|
| 0 | No drift; limb holds 90 (or 45) degrees for full 10 seconds. | | | | | | | | |
| 1 | Drift; limb holds 90 (or 45) degrees, but drifts down before full 10 seconds; does not hit bed or other support. | | | | | | | | |
| 2 | Some effort against gravity; limb cannot get to or maintain (if cued) 90 (or 45) degrees, drifts down to bed, but has some effort against gravity. | | | | | | | | |
| 3 | No effort against gravity; limb falls. | | | | | | | | |
| 4 | No movement. | | | | | | | | |
| UN | Amputation or joint fusion, explain: | | | | | | | | |
| | Score 5a: Left Arm 5b: Right Arm | | | | | | | | |

5

Instructions: The limb is placed in the appropriate position: hold the leg at 30 degrees (always tested supine). Drift is scored if the leg falls before 5 seconds. The aphasic patient is encouraged using urgency in the voice and pantomime but not noxious stimulation. Each limb is tested in turn, beginning with the non-paretic leg. Only in the case of amputation or joint fusion at the hip, the examiner should record the score as untestable (UN) and clearly write the explanation for this choice.

| Scale De | finition | | | | | | | |
|----------------------------------|--|--|--|--|--|--|--|--|
| 0 | No drift; leg holds 30-degree position for full 5 seconds. | | | | | | | |
| 1 | Drift; leg falls by the end of the 5-second period but does not hit the bed. | | | | | | | |
| 2 | Some effort against gravity; leg falls to bed by 5 seconds but has some effort against gravity. No effort against gravity; leg falls to bed immediately. No movement. Amputation or joint fusion, explain: | | | | | | | |
| 3 | | | | | | | | |
| 4 | | | | | | | | |
| UN | | | | | | | | |
| Score 6a: Left Leg 6b: Right Leg | | | | | | | | |

7 Limb Ataxia

Instructions: This item is aimed at finding evidence of a unilateral cerebellar lesion. Test with eyes open. In case of visual defect, ensure testing is done in intact visual field. The finger-nose-finger and heel-shin tests are performed on both sides, and ataxia is scored only if present out of proportion to weakness. Ataxia is absent in the patient who cannot understand or is paralyzed. Only in the case of amputation or joint fusion, the examiner should record the score as untestable (UN) and clearly write the explanation for this choice. In case of blindness, test by having the patient touch nose from extended arm position.

| Scale Def | Definition Absent. Present in one limb. Present in two limbs. | | | | | |
|---|---|--|--|--|--|--|
| 0 | | | | | | |
| 1 | | | | | | |
| 2 | | | | | | |
| UN Amputation or joint fusion, explain: | | | | | | |
| | | | | | | |

Score

6

Instructions: Sensation or grimace to pinprick when tested, or withdrawal from noxious stimulus in the obtunded or aphasic patient. Only sensory loss attributed to stroke is scored as abnormal and the examiner should test as many body areas (arms [not hands], legs, trunk, face) as needed to accurately check for hemisensory loss. A score of 2, "severe or total sensory loss," should only be given when a severe or total loss of sensation can be clearly demonstrated. Stuporous and aphasic patients will, therefore, probably score 1 or 0. The patient with brainstem stroke who has bilateral loss of sensation is scored 2. If the patient does not respond and is quadriplegic, score 2. Patients in a coma (item 1a=3) are automatically given a 2 on this item.

| Scale De | cale Definition | | | | | | |
|----------|---|--|--|--|--|--|--|
| 0 | Normal; no sensory loss. | | | | | | |
| 1 | Mild-to-moderate sensory loss; patient feels pinprick is less sharp or is dull on the affected side; or there is a loss of superficial pain with pinprick, but patient is aware of being touched. | | | | | | |
| 2 | Severe or total sensory loss; patient is not aware of being touched in the face, arm, and leg. | | | | | | |

Best Language

Instructions: A great deal of information about comprehension will be obtained during the preceding sections of the examination. For this scale item, the patient is asked to describe what is happening in the attached picture (p. 11), to name items on the naming sheet (p. 12), and to read from the list of sentences (p. 13). Comprehension is judged from responses here, as well as to all of the commands in the preceding general neurological exam. If visual loss interferes with the tests, ask the patient to identify objects placed in the hand, repeat, and produce speech. The intubated patient should be asked to write. The patient in a coma (item 1a=3) will automatically score 3 on this item. The examiner must choose a score for the patient with stupor or limited cooperation, but a score of 3 should be used only if the patient is mute and follows no one-step commands.

| Scale Definition | | | | | | | | |
|------------------|---|--|--|--|--|--|--|--|
| 0 | No aphasia; normal. | | | | | | | |
| 1 | Mild-to-moderate aphasia; some obvious loss of fluency or facility of comprehension, without significant limitation on ideas expressed or form of expression. Reduction of speech and/or comprehension, however, makes conversation about provided materials difficult or impossible. For example, in conversation about provided materials, examiner can identify picture or naming card content from patient's response. | | | | | | | |
| 2 | Severe aphasia; all communication is through fragmentary expression; great need for inference, questioning, and guessing by the listener. Range of information that can be exchanged is limited; listener carries burden of communication. Examiner cannot identify materials provided from patient response. | | | | | | | |
| 3 | Mute, global aphasia; no usable speech or auditory comprehension. | | | | | | | |

Score

Score

7

CLASP

10 Dysarthria

Instructions: If patient is thought to be normal, an adequate sample of speech must be obtained by asking patient to read or repeat words from the attached list (p. 12). If the patient has severe aphasia, the clarity of articulation of spontaneous speech can be rated. Only if the patient is intubated or has other physical barriers to producing speech, the examiner should record the score as untestable (UN) and clearly write the explanation for this choice. Do not tell the patient why he or she is being tested.

| Scale De | icale Definition | | | | | | | |
|----------|--|--|--|--|--|--|--|--|
| 0 | Normal. | | | | | | | |
| 1 | Mild-to-moderate dysarthria; patient slurs at least some words and, at worst, can be understood with some difficulty. | | | | | | | |
| 2 | Severe dysarthria; patient's speech is so slurred as to be unintelligible in the absence of or out of proportion to any dysphasia, or is mute/anarthric. | | | | | | | |
| UN | Intubated or other physical barrier, explain: | | | | | | | |

11 Extinction and Inattention

Instructions – Extinction and Inattention (formerly Neglect): Sufficient information to identify neglect may be obtained during the prior testing. If the patient has a severe visual loss preventing visual double simultaneous stimulation, and the cutaneous stimuli are normal, the score is normal. If the patient has aphasia but does appear to attend to both sides, the score is normal. The presence of visual spatial neglect or anosagnosia may also be taken as evidence of abnormality. Since the abnormality is scored only if present, the item is never untestable.

| stimulation in one of the se Profound hemi-inattentio | | | | |
|---|---|--|--|--|
| stimulation in one of the se Profound hemi-inattentio | No abnormality. | | | |
| Profound hemi-inattentio | Visual, tactile, auditory, spatial, or personal inattention, or extinction to bilateral simultaneous stimulation in one of the sensory modalities. Profound hemi-inattention or extinction to more than one modality; does not recognize own hand or orients to only one side of space. | | | |
| | | | | |

8

Score

Score

Total Score of Patient

| ITEM | SCORE |
|----------------|-------|
| 1a | |
| 1b | |
| 1c | |
| 2 | |
| 3 | |
| 4 | |
| 5 | |
| 6 | |
| 7 | |
| 8 | |
| 9 | |
| 10 | |
| 11 | |
| TOTAL SCORE | |

9

© Apex Innovations

11

NIH Stroke Scale

MAMA

TIP-TOP

FIFTY-FIFTY

THANKS

HUCKLEBERRY

BASEBALL PLAYER

CATERPILLAR

12

NIH Stroke Scale

You know how.

Down to earth.

I got home from work.

Near the table in the dining room.

(13)

They heard him speak on the radio last night.

NIH Stroke Scale

Appendix 7: Short form Stroke Impact Scale (SIS)

| In the past week, how would you rate the strength of your leg that was most affected by your stroke? |
|---|
| In the past week, how difficult was it for you to think quickly? |
| In the past week, how often did you feel that you have nothing to look forward to? |
| In the past week, how difficult was it to understand what was being said to you in a conversation? |
| In the past 2 weeks, how difficult was it to do light household tasks/chores (eg, dust, make a bed, take out the rubbish, do the dishes)? |
| In the past 2 weeks, how difficult was it to walk without losing balance? |
| In the past 2 weeks, how difficult was it to use your hand that was most affected by your stroke, to pick up a coin? |
| During the past 4 weeks, how much of the time have you been limited in your social activities? |
| |
| Score each statement from 1 to 5: 1 = Could not do at all; |
| 2 = very difficult; |
| 3 = somewhat difficult; |
| 4 = a little difficult; |
| 5 = not difficult at all. |

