10.3.3 Secondary outcome analysis

Secondary outcome measures will be analysed using the following methods:

- Mortality at 90 days will be analysed using Cox proportional hazards models.
- Any urgent or unplanned re-admission to 90 days and recurrent stroke or vascular events will be analysed using logistic regression.
- Home time, stroke-related health status, health and social care resource use and caregiver burden will be analysed using general linear models.
- EQ-5D-5L at 90 days will be compared between treatment groups using a general linear model adjusted for the baseline EQ-5D-5L.
- Length of stay will be analysed using a negative binomial model.

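### Appendix 7 gives one difficulty key for all eight Stroke Impact Scale items, although three of them ask about strength or frequency

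*Protocol*

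**What the plan says.** Protocol Appendix 7 lists eight SIS items and then a single scoring instruction, "Score each statement from 1 to 5: 1 = Could not do at all", with the top anchor "5 = not difficult at all". The three points between are also degrees of difficulty. The instruction covers each statement and names no exception.

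The item stems differ in kind. One that suits the key is "how difficult was it for you to think quickly". Three that do not are:

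- "how would you rate the strength of your leg that was most affected by your stroke"
- "In the past week, how often did you feel that you have nothing to look forward to"
- "During the past 4 weeks, how much of the time have you been limited in your social activities"

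The SIS is a secondary outcome at 90 days (section 3.3.2). Section 13.3 records that it was added after the second patient and public workshop agreed that a more stroke-related patient-reported measure was needed. Section 7.6 has it collected by trained central staff, blinded to allocation, by video or telephone. Section 3.3 says the scales can also be collected by post. Under section 11.1 the assessor's eCRF entry is the source record, or the paper form where a postal questionnaire is used. On analysis, section 10.3.3 says: "Home time, stroke-related health status, health and social care resource use and caregiver burden will be analysed using general linear models".

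**The concern.** A difficulty scale cannot answer a question about strength, or about how often something happened. Whoever records the answer to those three items has to translate it into a number from 1 to 5 by a rule the protocol does not give. Different assessors may translate differently, and so may a postal respondent with nobody there to explain.

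Direction is a second problem for the two frequency items. The key makes 5 the best state. Both items describe something bad, so a respondent who simply counts upward in frequency would give the worst state a 5. Appendix 8, the caregiver burden scale collected at the same central assessment, does score ascending frequency with higher meaning worse, so an upward count would be a natural habit to carry over.

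At stake is the precision of the trial's stroke-specific patient-reported outcome. Because the eCRF entry is itself the source, a bare number would not show later how a frequency answer had been mapped, so the analysis could not repair it.

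**Working it through.** The protocol states no figure for this point, so there is none to reproduce. The check sets each stem in Appendix 7 against the one printed key.

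| Item | Subject | What the stem asks | Fits the difficulty key? |
|---|---|---|---|
| 1 | Strength of affected leg | A rating of strength | No |
| 2 | Thinking quickly | How difficult | Yes |
| 3 | Nothing to look forward to | How often | No; more often is worse |
| 4 | Following conversation | How difficult | Yes |
| 5 | Light household tasks | How difficult | Yes |
| 6 | Walking with balance | How difficult | Yes |
| 7 | Picking up a coin | How difficult | Yes |
| 8 | Limited social activities | How much of the time | No; more time is worse |

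**Count.** Five items fit and three do not. 3 / 8 = 37.5% of the items. This is a share of items. It would be a share of the score only under equal weighting, and the protocol prints no totalling rule for the SIS.

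**Direction.** Take a participant who never has the feeling in item 3. If the assessor keeps the key's direction (5 best), the item scores 5. If the assessor counts frequency upward (1 = never, 5 = always), the same answer scores 1. Item 8 behaves the same way. Nothing in the appendix tells the assessor which to do, beyond the fact that the difficulty key itself runs toward 5 as best.

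**Search for a remedy elsewhere.** No other section of the protocol gives strength anchors, frequency anchors or a reverse-scoring rule for the SIS. The contrast with Appendix 8 is instructive: there the response columns are frequencies that match the questions, and a totalling instruction is printed.

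**The case against.** The strongest reply is that the printed key does fix a direction. Since 5 is the best state, a trained assessor can still place leg strength or social limitation in order from worst to best, and nobody need reverse anything. Collection is by trained central staff, with post as a fallback (section 3.3.1 says so for the mRS), which limits improvisation. The assessors are blinded, so inconsistent coding should blur the comparison, not favour an arm. The eCRF and postal form may already carry the right options for each item. All of this is fair and limits the point. It does not remove it, because Appendix 7 as written still applies a difficulty key to three questions that are not about difficulty.

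A reader might infer something stronger: that three-eighths of the score is invalid, or that the treatment contrast could be halved. The arithmetic behind such a claim is simple. With equal weights and an equal effect on every item, reversing two of eight items in a fraction q of interviews multiplies the contrast by 1 − 2q(2/8) = 1 − 0.5q, which is 0.875 at q = 25%, 0.75 at q = 50% and 0.50 at q = 100%. If all three items carried no signal, 5/8 = 62.5% would remain. The documents support neither claim. They give no value for q and no weighting, and q = 100% would need every interview to go against the printed direction. Ill-fitting labels reduce reliability; they do not remove all information. These factors are hypothetical and should not be reported as the size of the problem.

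A reader might also infer that the scale departs from the published short form cited in section 3.3, or that the trial's forms copy Appendix 7. Neither the publication nor the forms are at hand, so neither claim can be made.

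**Conclusion.** The point holds as an error in a stated scoring rule. Three of the eight SIS items have no fitting response option under the printed key, and two of those three could be coded inconsistently in direction. The likely consequence is extra noise and some attenuation in one of the twelve secondary outcomes listed in section 3.3.2, of a size that cannot be estimated from the documents. There is no ground to expect bias between arms, provided blinding of the assessors holds. The primary mRS analysis, the sample size and the interim rules are unaffected.

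This is not detail that can wait for the statistical analysis plan. The protocol itself states the response key, and the key acts when the data are collected. The conclusion rests only on the wording of Appendix 7 and on the absence of other SIS anchors in the protocol. If the eCRF and postal form already carry suitable options, what remains is a protocol text that contradicts the trial's own forms.

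**What to change.** Replace the single key in Appendix 7 with 5-point response options for each item, taken from the cited instrument: strength options for the leg item, frequency options for the two items on how often and how much of the time, and difficulty options for the other five. State that every item is coded so that 5 is best, and say explicitly that this includes the two negatively worded frequency items. Then check that the eCRF and the postal form show the same options and the same coding before Day 90 data are collected. How the total is formed can be left to the statistical analysis plan.

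The cost is one appendix correction and a check of form labels. No extra data, visits or participants are needed.
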